6.4 Pharmacokinetic Data Summarization and Presentation

SAS software (version 9.4, Cary, North Carolina) will be used for all data presentation and summarization including statistical analyses, summary tables, graphs, and data listings.

Plasma nicotine concentrations (observed and background-corrected,) λ_z (observed only) and other PK parameters (background corrected only) will be summarized with descriptive statistics including number of subjects (n), number and percent of subjects with missing data (Missing, n (%)), arithmetic mean (Mean), standard deviation (SD), percent CV (CV%), standard error of the mean (SEM), 95% confidence interval (95%CI), minimum, first quartile (Q1), median, third quartile (Q3), and maximum. Summaries will be further stratified by Sex.

In addition, geometric mean (Geo. Mean), 95% geometric confidence interval (Geo. 95% CI) and geometric CV (Geo. CV%) will be presented as well, as applicable.

For observed plasma nicotine concentrations, the number and percent of values below LLOQ (BLQ, n(%)) or above ULOQ (ALQ, n(%)) will be presented in each summary table.

Categorical variables will be summarized by frequency statistics (number and percentage).

For endpoints relating to sampling times (e.g., T_{max}) only median, Q1, Q3, minimum and maximum will be presented.

All analyses and summaries will be performed by product and overall.

The analytical data will be presented in the tables/listings to the same precision as received from the analytical laboratory.

The level of precision and rounding for the summary statistics listed in [Section 14.1.5](#).

Where individual data points are missing because of dropouts or other reasons, the data will be summarized based on reduced denominators. Missing PK data will be treated as missing and no data imputation will be conducted.

Mean and individual plasma nicotine concentrations will be presented graphically (linear and semi-log plots; linear plots will be presented with and without SD).

6.5 Statistical Analysis of PK Parameters

6.5.1 Main analysis

A mixed model analysis of variance (ANOVA) will be performed on the natural log (ln)-transformed nicotine PK parameters AUC_{0-2min} , AUC_{0-4min} , AUC_{0-Tmax} , AUC_{0-10h} , AUC_{0-last} , $AUC_{0-infinity}$, $\max(C_t/t)_{t \in [0, Tmax]}$ and C_{max} .

The model will include terms for sequence, period, product exposure as fixed effects and subject as a categorical random effect modeling the within subject correlations.

The results of this analysis for each of are presented in terms of geometric least square ratios and 95% confidence intervals for the P4M3 Gen 2.0:Cigarettes ratio.

This approach is consistent with the guidelines in the European Medicines Agency's guidelines for bioequivalence investigations and FDA's Center for Drug Evaluation and Research.

Philip Morris Products S.A.
P4M3 Gen 2.0, P4-PK-04-US

██████████ Statistical Analysis Plan Number CA34617

The analysis of T_{max} will be performed by conducting a Wilcoxon signed rank test and calculating the median T_{max} for each product along with the Hodges-Lehmann estimate of the median difference between products, and the related 95% CI.

The ANOVA analysis will be performed using the following SAS code:

```
PROC MIXED data=<> method=REML;
class subject sequence period product;
model log(parameter) = sequence period product/ddf=KR;
repeated product / subject=subject type=csh;
lsmeans product / pdiff=control("CC") cl alpha=0.05;
run;
```

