A mixed model analysis of variance (ANOVA) will be conducted on AUC_{0-2min} , AUC_{0-4min} , AUC_{0-Tmax} , AUC_{0-10h} , AUC_{0-last} , $AUC_{0-infinity}$, $\max(C_t/t)_{t \in [0, T_{max}]}$ and C_{max} endpoints in the natural logarithmic scale. The results of this analysis will be presented in terms of geometric least square mean ratios and 95% confidence intervals (95% CI) for the P4M3 Gen 2.0: cigarettes ratio and the ratios of variants of P4M3 Gen 2.0.

Confidentiality Statement

Data and information contained in this document are considered to constitute trade secrets and confidential commercial information, and the legal protections provided to such trade secrets and confidential information are hereby claimed under the provisions of applicable law. No part of this document may be publicly disclosed without the written consent of Philip Morris Products S.A.

The analysis of T_{max} will be conducted using non-parametric tests and Hodges-Lehmann estimates of median difference with its derived 95% CI.

Sample Size:

The sample size is empirically based as there are no considerations for statistical hypothesis.

A total of 36 subjects is expected to be sufficient to obtain a precision of 0.55 or less on the P4M3 Gen 2.0 : cigarettes C_{max} ratios.

Confidentiality Statement

Data and information contained in this document are considered to constitute trade secrets and confidential commercial information, and the legal protections provided to such trade secrets and confidential information are hereby claimed under the provisions of applicable law. No part of this document may be publicly disclosed without the written consent of Philip Morris Products S.A.

TABLE OF CONTENTS

1	ETHICS AND REGULATIONS	24
1.1	Independent Review Board (IRB) Approval	24
1.2	Ethical Conduct of the Study	25
1.3	Subject Information and Consent.....	25
1.3.1	Informed Consent Form for Study Participation	25
1.3.2	Amendment to the Informed Consent Form	25
1.4	Good Clinical Practice and Regulatory Requirements	26
2	INTRODUCTION	27
2.1	Background.....	27
2.1.1	Smoking-Related Diseases and Harm Reduction Strategy	27
2.1.2	Description of the Product and Scientific Findings	28
2.2	Purpose of the Study	29
2.3	Anticipated Benefits and Risks.....	29
2.3.1	Anticipated Benefits.....	29
2.3.2	Anticipated Foreseeable Risks due to Study Procedures	29
2.3.3	Anticipated Foreseeable Risks due to Investigational Product.....	29
2.3.4	Unforeseeable Risks.....	30
3	STUDY OBJECTIVES.....	31

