12.2.2 Method

The analysis of confidence interval precision on the P4M3 Gen 2.0: cigarettes C_{max} ratios has been implemented using SAS, simulating 10000 sets of log-transformed data for 36 subjects with the assumptions described in section 12.2.1, the 3 periods and the 6 sequences of this cross-over design.

The statistical analysis has been performed with a linear model with repeated measurement including as fixed effect the sequence, the period, and the product exposure.

The P4M3 Gen 2.0:cigarettes C_{max} ratios and related confidence intervals have been determined by using the exponential of the difference between P4M3 Gen 2.0 variants and cigarettes on the log-transformed data.

Then precision has been determined as the 90th percentile of the 95% confidence interval of the P4M3 Gen 2.0: cigarettes C_{max} ratios.

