11. SUMMARY OF CHANGES FROM PROTOCOL-PLANNED ANALYSIS

Per protocol, demographics, baseline characteristics, pharmacokinetics endpoints, pharmacodynamics endpoints, human puffing topography parameters, amount of nicotine

Philip Morris Products S.A.
P4M3 Gen 2.0, P4-PK-04-US

██████████ Statistical Analysis Plan Number CA34617

delivered, will be analyzed using the randomized and PK population. They will be analyzed only in the PK population. The randomized population will not be defined.

Where comparisons between CA35 and Cigarettes, and between CM35 and Cigarettes, are performed, the comparison between CA35 and CM35 will be performed additionally.

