Geometric least-squares means (LSMs) are calculated by exponentiating the LSMs derived from the ANOVA.

Geometric Mean Ratio (GMR) = 100*(test/reference)

Intra-subject CV% was calculated as 100 x square root(exp[MSE]-1), where MSE = Residual variance from ANOVA.

Source: Table XXXX

Philip Morris Products S.A.
P4M3 Gen 2.0, P4-PK-04-US

████████ Statistical Analysis Plan Number CA34617

Notes for Generating the Actual Table:

* See [Section 6.5](#) for the parameters to be included.

Presentation of Data:

- The following PK parameters will be presented in the following order and with the following units:
 - Table 4 and Table 15.2.2.1.4: C_{\max} <ng/mL>, AUCs <ng*min/mL>, $\max(C_t/t)_{t \in [0, T_{\max}]}$ <ng/mL/min>
- n will be presented as an integer (with no decimal).
- See [Section 6.4](#) for statistic presentation.

Philip Morris Products S.A.
P4M3 Gen 2.0, P4-PK-04-US

████████ Statistical Analysis Plan Number CA34617

In-Text Table 5 and post-text Table 15.2.2.1.5 will have the following format, and Table 15.2.2.1.5.1 a similar format:

Table 5 Statistical Comparisons of Plasma Nicotine PK Parameter T_{max} for P4M3 Gen 2.0 and Cigarettes (PK Population)

Parameter	Comparison (Test vs Reference)	Test	Reference	-----Difference Test – Reference-----	
		Median (n)	Median (n)	Median	95% Confidence Interval
T_{max}	CA35 vs Cigarette	X.XX (X)	X.XX (X)	X.XX	X.XXXX - X.XXXX
T_{max}	CM35 vs Cigarette	X.XX (X)	X.XX (X)	X.XX	X.XXXX - X.XXXX
T_{max}	CM35 vs CA35	X.XX (X)	X.XX (X)	X.XX	X.XXXX - X.XXXX

CA35 = < >

CM35 = < >

PK Population = Subset of the safety population including all randomized subjects without major protocol deviations impacting the evaluability of the main objectives and for whom at least one nicotine PK parameter can be derived

For the difference calculation, the first product in the comparison is the test and the second product in the comparison is the reference.

The 95% confidence interval is constructed using Walsh Averages and appropriate quantile on the normal approximation of the Wilcoxon Signed Rank test statistic.

Median is the point estimate of the Hodges-Lehmann median difference.

Notes for Generating the Actual Table:

Presentation of Data:

- See [Section 6.4](#) for data presentation.

Philip Morris Products S.A.
 P4M3 Gen 2.0, P4-PK-04-US
 [REDACTED] Statistical Analysis Plan Number CA34617

In-text Table 6 will have the following format:

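### SAP 6.5.1 text, its SAS code and the Table 4 footnote describe different models: the intra-subject CV column has no defined input and the CM35 vs CA35 contrast is not requested

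*SAP*

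**What the plan says.** **Model in the text.** SAP 6.5.1 and protocol 12.5.4.1 both give fixed effects for sequence, period and product, with "subject as a categorical random effect modeling the within subject correlations".

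**Model in the code.** SAP 6.5.1 then says the ANOVA will be run with the SAS code it prints. That code has no RANDOM statement. Its covariance line is "repeated product / subject=subject type=csh", its MODEL line is "model log(parameter) = sequence period product/ddf=KR", and its contrast line is "lsmeans product / pdiff=control('CC') cl alpha=0.05".

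**Model used for sizing.** Protocol 12.2.2 describes a "linear model with repeated measurement including as fixed effect the sequence, the period, and the product exposure", so the protocol does not settle which form was intended.

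**CV column.** The Table 4 footnote in SAP 14.2 reads: "Intra-subject CV% was calculated as 100 x square root(exp[MSE]-1), where MSE = Residual variance from ANOVA". Table 15.2.2.1.4 shares this format, and the by-sex Table 15.2.2.1.4.1 is to be similar.

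**Comparison between variants.** The protocol synopsis (Statistical Methods) plans intervals for "the ratios of variants of P4M3 Gen 2.0". SAP Section 11 says "the comparison between CA35 and CM35 will be performed additionally". The Table 4 shell prints CM35 vs CA35 rows with a ratio, an interval and a CV. The results sentence in SAP 6.5.1 names only the ratio to cigarettes.

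**The concern.** This is the only program prescribed for the main PK comparison table, and the sensitivity analyses in SAP 6.5.2 are to be run in the same way. Followed literally, it leaves two parts of that table unfilled.

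First, a random-subject model has one residual variance and heterogeneous compound symmetry (CSH) has none, so the footnote's formula has nothing to act on. SAP Section 11, which lists departures from the protocol, does not mention the change of covariance structure. Someone would have to choose a substitute at programming time without documentation.

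Second, `pdiff=control` returns only differences from one level. The point ratio of CM35 to CA35 could be formed from the printed least-squares means. Its confidence interval could not be recovered from the two control contrasts, because their covariance is not shown.

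Two smaller code faults need the same edit. CC is not a product label used in the SAP (the labels are CA35, CM35 and Cigarettes). `ddf=KR` is not the Kenward-Roger option, which SAP 7.3 writes as `ddfm=KR`.

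**Working it through.** **Plan figures.** The plan states no intra-subject CV, so there is none to reproduce. The precision of 0.55 in protocol 12.2 is not used here. On the stated inputs, the 90th percentile of the full interval width comes to 0.31 to 0.33, but the protocol does not define precision exactly and that is a separate question.

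**Inputs (protocol 12.2.1, Cmax).** GCV 80% for all products (cited range 63% to 83%); log-scale within-subject correlation 0.8 (cited range 0.82 to 0.88). N is 36.

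**Row count.** Six AUCs, Cmax and max(Ct/t) make 8 parameters. With 3 comparisons that is 8 x 3 = 24 rows; the shell prints nine lines because one AUC line stands for all six. The code requests at most 8 x 2 = 16 contrasts, leaving 8. If the by-sex table is fitted separately for each sex (an assumption), it adds 2 x 24 = 48 rows, 16 of them not requested.

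**CV at the planning values.** CV = 100 x sqrt(exp(v) - 1).

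- Total log variance: ln(1 + 0.80²) = 0.4947. Used as v, this gives 80.0%.
- Within-subject variance: 0.4947 x (1 - 0.8) = 0.0989. Used as v, this gives 32.2%.

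Each variance that CSH reports is a total variance, so entering one as the MSE would give the first figure.

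**CV over the cited ranges.**

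| GCV | Total log variance | Total CV | Within-subject CV, correlation 0.82 | Within-subject CV, correlation 0.88 |
|---|---|---|---|---|
| 63% | 0.3343 | 63% | 24.9% | 20.2% |
| 83% | 0.5241 | 83% | 31.5% | 25.5% |

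**Do the two legitimate definitions agree?** Under CSH a pairwise within-subject variance is w = (s1² + s2² - 2·rho·s1·s2)/2. With equal variances it equals the random-subject residual. In 300 simulated complete trials at the planning values, the ratio estimates against cigarettes were identical under the two models, the mean SE of the log ratio was 0.0727 under both, and both CVs averaged 31.6%. The averaged CSH variances gave 79.5%.

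With unequal variances the two definitions separate. As an illustration, assume cigarettes at GCV 83%, both variants at 63%, and correlation 0.8:

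- Variant vs cigarettes: w = (0.3343 + 0.5241 - 1.6 x 0.4185)/2 = 0.0943, CV 31.5%.
- CM35 vs CA35: w = 0.2 x 0.3343 = 0.0669, CV 26.3%.
- Random-subject residual (mean variance minus mean covariance): 0.3975 - 0.3124 = 0.0852 before rounding, CV 29.8%.

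The interval widths move too. With SE = sqrt(2v/36), variant vs cigarettes has 0.0724 under CSH and 0.0688 under the pooled residual (about 5% larger). CM35 vs CA35 has 0.0609 and 0.0688 (about 11% smaller).

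**Missing interval.** At the planning values, the SE of any pairwise log difference is sqrt(2 x 0.0989/36) = 0.0741. Combining the two control contrasts as if they were independent would give 0.0741 x sqrt(2) = 0.1048, which is wrong. The contrast has to be requested from the model.

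**The case against.** The strongest reply is that little of substance is affected. The printed code is evidently a template, with an empty dataset name and a generic response, and would be corrected when programmed. The CM35 vs CA35 comparison is already pre-specified elsewhere, and once a model is fixed its estimate and interval follow with no further choice. Intra-subject CV is neither an endpoint nor tied to a hypothesis. A random subject intercept and plain compound symmetry imply the same covariance when the correlation is not negative, so CSH adds only unequal variances. The 80.0% figure needs a mistake that the SAP does not direct. The 31.5/26.3/29.8% spread needs a split of GCVs that the protocol does not make. The SAP may be amended until database lock, and it says its table shells may change.

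Much of this stands. The template look can excuse the CC label and `ddf`. The missing contrast is an omission in the code and in the 6.5.1 results sentence, and its definition is not in doubt. The CV comparisons are conditional and are offered as such.

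It does not settle which model governs or what replaces the MSE. `type=csh` is a specific covariance choice that conflicts with the sentence above it, and no section defines a CV under it. That the SAP can be amended before lock is a reason to amend it.

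**Conclusion.** The concern holds. The text, code and footnote in SAP 6.5.1 and 14.2 cannot all be followed. Under the prescribed code, the CV input is undefined in all 24 Table 4 rows, and the contrast and interval for 8 of them (CM35 vs CA35) are not requested.

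The comparisons with cigarettes are not invalidated. CSH accounts for the within-subject correlation, and with equal variances and complete data the two models agree.

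The CV at stake is 32.2% against 80.0% at the planning values if a total variance is used in error. Between the two legitimate definitions there is no material difference at equal variances, and a gap of a few percentage points under the assumed unequal case. That case also shifts the SEs by about +5% and -11%. It is an illustration; the protocol assumes 80% for every product.

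This should be corrected before lock as a matter of reconciliation.

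**What to change.** Choose one model and make the three places agree.

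- **Option A, as the text says.** Replace the REPEATED line with `random subject(sequence);` and keep the residual-based footnote.
- **Option B, as the code says.** Keep CSH, amend the 6.5.1 sentence to describe it, and list it in SAP Section 11 as a departure from protocol 12.5.4.1. Redefine the CV for each comparison as 100 x sqrt(exp(w) - 1), with w = (s1² + s2² - 2·rho·s1·s2)/2.

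Under either option:

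- use `lsmeans product / pdiff cl alpha=0.05;` to obtain all pairs, or keep the control form and add an ESTIMATE statement for CM35 minus CA35;
- name the comparison between variants in the 6.5.1 results sentence;
- use the actual product labels and `ddfm=KR`.

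The cost is a few lines of code, a sentence or two of text and, under Option B, one footnote. No data collection or sample size changes.

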6.5.2 Sensitivity Analysis

In case of any uncorrected nicotine concentration at T_0 [μC_0] greater than 5% of their uncorrected maximum value, a sensitivity analysis of the endpoints will be performed similarly to the main analysis, whereby data of these subjects for this specific study day will be excluded from the analysis.

In case the plasma concentrations cannot be background-corrected in 2 or more subjects in a sequence a sensitivity analysis will be performed similarly to the main analysis, whereby

- If the subject's terminal elimination rate cannot be estimated it will be substituted by the average terminal elimination rate of the subjects having the same sex,
- If the uncorrected nicotine concentration at baseline is not available for the Period 2 or 3, it will be substituted by the extrapolation of the previous concentrations using the terminal elimination rate.

7. PHARMACODYNAMIC EFFECTS (SUBJECTIVE EFFECTS AND RELATED BEHAVIORAL ASSESSMENTS)

7.1 Data Collection

7.1.1 ABOUT-Product Experience Questionnaire

Product Experience will be assessed via a subject self-reported outcome measure at the time point described in [Table 3](#), using the Assessment of Behavioral Outcomes related to Tobacco and nicotine products (ABOUT) - Product Experience questionnaire ([Cappelleri et al, 2007](#)), part of the ABOUT Toolbox.

The questionnaire consists of three multi-item scales and two single-item scales, arising from an adaptation and rewording of the modified cigarette evaluation questionnaire (mCEQ) to RRP and the Product Evaluation Scale ([Hatsukami, D.K., et al., 2013](#)).

The questionnaire assesses the degree to which subjects experience the reinforcing effects of P4M3 Gen 2.0 with CA35 and CM 35 Cartridges and Cigarettes by measuring:

Philip Morris Products S.A.
P4M3 Gen 2.0, P4-PK-04-US

██████████ Statistical Analysis Plan Number CA34617

- Product satisfaction (satisfying, tastes good, enjoy the product): average of the response scores from questions 1, 2, and 12.
- Psychological rewards (calms down, more awake, less irritable, helps concentrate, reduces hunger): average of the response scores from questions 4 to 8.
- Aversion (dizziness, nausea): average of the response scores from questions 9 and 10.
- Enjoyment of respiratory tract sensations (single-item assessment): response score from question 3.
- Craving reduction (single-item assessment): response score from question 11.

Subjects will be asked to assess the 12 items of the questionnaire on a 7-point scale, ranging from “not at all” to “extremely”.

Responses on the 7-point scales, where 1 = not at all and 7 = extremely, for each ABOUT questionnaire will be treated as a continuous variable and used to calculate the factor scores.

7.1.2 VAS Craving Assessment

Cigarette craving will be assessed using a 1 item self-reported craving VAS, asking subjects to rate craving for cigarettes (How strong is your craving for cigarettes?), on a 100 mm unipolar scale, ranging from 0 (no craving), to 100 (strong craving). On Day 1 to Day 3, VAS craving assessment will be collected at: Within 15 minutes prior to T_0 , after T_0 at 4 minutes \pm 1 minute, 10 minutes \pm 1 minute, 15 minutes \pm 1 minute, 30 minutes \pm 2 minutes, 1 hour \pm 5 minutes, 2 hours \pm 5 minutes, 4 hours \pm 5 minutes, 10 hours \pm 5 minutes.

7.1.3 VAS Liking Assessment

Cigarette and P4M3 Gen 2.0 liking will be assessed using a one item self-reported liking VAS, asking subjects to rate liking for product (At this moment, my liking for this product is:) on a 100 mm bipolar scale, ranging from 0 (strong disliking), to 100 (strong liking), with a neutral middle point, as recommended in the FDA guidance for industry on abuse liability assessment. On Day 1 to Day 3, VAS liking assessment will be collected at the following time points: after T_0 at 4 minutes \pm 1 minute, 10 minutes \pm 1 minute, 15 minutes \pm 1 minute, 30 minutes \pm 2 minutes, 1 hour \pm 5 minutes, 2 hours \pm 5 minutes, 4 hours \pm 5 minutes, 10 hours \pm 5 minutes.

7.2 Data Summarization

Descriptive statistics (n, mean, SD, CV%, SEM, minimum, Q1, median, Q3, maximum, and 95% confidence interval) of the ABOUT-Product Experience questionnaire subscale scores and VAS craving and VAS liking assessments will be provided by study product and time points, when applicable. Change from baseline (pre-product use) for VAS craving score will be summarized by study product and time point. Individual responses will be listed. Summaries will be further stratified by Sex.

7.3 Inferential Analysis

An analysis of covariance (ANCOVA) will be conducted by product use. The PK parameters will be transformed in the natural logarithmic scale. The model will include terms for sequence, period and product liking by the VAS-liking assessment. The effect of VAS-liking will be analyzed in different models with VAS-liking at T_1 (after 4 minutes), T_2 (after 10 minutes), and T_3 (after 15 minutes). The results of this analysis will be presented by product in terms of:

- The percentage of variance explained by product liking by the VAS-liking assessment.
- The standardized effect of product liking by the VAS-liking assessment on the endpoint, defined as the mean effect divided by the square root of its variance.

The ANCOVA analysis will be performed using the following SAS code:

```
PROC MIXED data=<> method=type3;  
By product;  
class subject sequence period;  
model log(PK parameter) = sequence period liking_score/ddfm=KR solution;  
run;
```

Another analysis of covariance (ANCOVA) will be conducted similarly to the above with the exception that it will be performed overall using mixed effects ANCOVA where the model will include, in addition, the subject as a categorical random effect to model the within subject correlations.

The same model will also be used to perform the analysis for human puffing topography parameters (total number of puffs, total puff volume, and total puff duration) to estimate the effect of VAS-liking score on the topography parameters.

